**Table 9-3 Estimated NT-814 exposures at steady state**

Dose	AUC 0-last at Steady State		
	Lower bound 95% CI	Geometric Mean	Upper Bound 95% CI
40 mg	2,390	2,740	3,150
80 mg	4,780	5,500	6,310
120 mg	6,760	8,240	9,460
160 mg	9,580	10,990	13,350

AUC0-24 = Area under the plasma concentration-time curve from 0 to 24 hours, CI = confidence interval

These four doses enable a range of exposures to be evaluated that encompass the full range of effectiveness responses observed in RELENT-1. The mean values at the mid doses (80 and 120 mg) are around the point that exposure-response modelling predicts maximum efficacy and the low and high doses are, respectively, expected to enable the rising and plateau parts of the dose-response curve to be demonstrated.

The upper bound of the confidence interval for predicted exposure at the high dose is below the mean exposure for the high dose in the RELENT-1 study (~15,000 ng\*hr/ml) and is substantially below the individual highest exposures (up to ~80,000 ng\*hr/ml) that were well tolerated in that study. It is also below the mean (~14,000 ng\*hr/ml) and maximum (~42,000 ng\*h/mL) values observed in healthy males after repeat dosing for 4 weeks that were also well tolerated with no safety concerns.

Thus, the administration of these four dose levels together with sparse PK sampling in this study will allow a robust evaluation of both the dose-response and PK exposure-response, from which it will be possible to select an appropriate dose to progress into the pivotal Phase 3 registration studies.

## 9.2 Investigational medicinal product

The IMP will consist of NT-814 40 mg capsules or matching placebo. The capsules are oblong, soft-gelatin capsules and each subject will take 4 capsules orally once-daily. The number of active and placebo capsules that each subject will take will be dependent on the dose to which they have randomized:

Dose	IMP Supply
Placebo	4 x placebo capsules
40 mg NT-814	1 x NT-814 capsule, 3 x placebo capsules
80 mg NT-814	2 x NT-814 capsules, 2 x placebo capsules
120 mg NT-814	3 x NT-814 capsules, 1 x placebo capsule
160 mg NT-814	4 x NT-814 capsules

Inactive ingredients in both the NT-814 capsules and the placebo capsules are Capmul MCM EP, Labrasol ALF, Tween 80, Peceol and Vitamin E.

The physical, chemical, pharmaceutical formulation properties and characteristics of the IMP are described in the IB.

All capsules will be blistered and packaged into weekly cards, with each weekly card containing capsules for a 7-day week plus an additional day for overage. These weekly cards will be further packaged into cardboard cartons:

- For the single-blind placebo run-in period, a carton will be dispensed containing 2 weekly placebo cards thereby providing sufficient capsules for the 2-week period between Screening Visit 2 and the Baseline visit (plus 2 days overage to allow for delays in clinic visit scheduling).
- For the post-randomisation double-blind treatment phase, each carton will contain 4 weekly cards thereby providing sufficient capsules for a 4-week dosing period (plus 4 days overage to allow for delays in clinic visit scheduling).

The IMP cards and cartons will be labelled in accordance all applicable local regulatory requirements. Multi-language labels may be applied to the IMP.

All IMP must be stored in a secure area with access limited to the Investigator and authorized site staff. The IMP is to be shipped and stored at controlled room temperature and be protected from light.

Only authorized investigational site study staff members are to dispense the IMP.

### **9.3 Allocation to Treatment**

The 2-week placebo-run in period will be conducted in a single-blind manner, with the subjects blinded to the treatment allocated.

The post-randomisation 12-week treatment phase of the study will be conducted in a double-blind manner, with the subjects, Investigators and Sponsor all blinded to the treatment allocated. Both NT-814 and placebo will be presented as soft-gel capsules, identical in size and shape.

On successful completion of screening and confirmation of eligibility, subjects will initially be randomised in a 1:1:1:1:1 ratio to receive either NT-814 40 mg/day, 80 mg/day, 120 mg/day, 160 mg/day or placebo. Randomisation will be stratified by region (North America or Europe). After completion of the first interim review the randomisation may be changed (see Section 11.2). Regardless of any changes to the randomisation ratio, subjects will continue to receive the dose regimen they were randomised to for the full 12-week treatment period.

The IMP each subject will receive will be allocated by an IWRS tool provided by Pharm Olam on behalf of the Sponsor.

## **9.4 Study Treatment and Administration**

IMP will be taken once daily both during the 2-week placebo run-in phase and the 12-week double-blind treatment phase.

For the placebo run-in, the first dose will be taken in the clinic at Screening Visit 2 and the last dose will be taken the evening before the Baseline visit.

For the double-blind treatment phase, the first dose will be taken in the clinic at the Baseline visit (Day 1) and the last dose will be taken the evening before the Week 12 visit. IMP doses are fixed and will not be adjusted for individual subjects during the study.

Subjects will be required to take 4 capsules of IMP once-daily in the evening before bedtime.

At Screening Visit 2, Baseline, Week 4 and Week 8 subjects will be dispensed sufficient IMP for daily dosing at home until the next visit, with overage included to allow for visit windows.

At Screening Visit 2, subjects will be dispensed sufficient supply to cover the period to the Baseline visit.

At the Baseline visit subjects will be dispensed sufficient supply to cover the period to Week 4. An interim check of compliance will be made at the Week 2 visit (subjects will be instructed to bring their IMP carton with them to this visit).

At the Week 4 visit subjects will be dispensed sufficient supply of IMP to cover the period from Week 4 to Week 8.

At the Week 8 subjects will be dispensed sufficient supply of IMP to cover the period from Week 8 to Week 12.

On the days of clinic visits (Baseline, Weeks 2, 4, 8, and 12) subjects will be asked to provide the time that they took their dose the previous evening and this will be documented in the eCRF.

All doses are to be taken at approximately the same time each evening. If a subject forgets to take a dose in the evening then the dose can be taken at any time up until 9 a.m. the following day. After this time, the dose should not be taken and will be considered a missed dose.

Subjects will return any unused medication at each clinic visit.

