#### **8.6.5 Baseline (Day 1)**

Subjects will return to the clinic for the Baseline visit at which compliance with eDiary completion and hot flush data will be reviewed. Subjects who comply with all other selection criteria, who have completed the diary for at least 9 days, and who have recorded an average of at least 7 moderate or severe hot flushes per day (including night-time) over the last 7 days that the eDiary was completed may enter the 12-week double-blind portion of the study and be randomised to one of 40 mg, 80 mg, 120 mg or 160 mg NT-814 or placebo treatments. The mean number of hot flushes will be calculated programmatically by the eDiary vendor and the outcome made available to the site.

Subjects who **do not** record an average of at least 7 moderate or severe hot flushes per day (including night-time) over the last 7 days that the eDiary was completed, or who are not compliant with eDiary completion will be deemed Screen Failures and will not be able to continue into the study. Limited data will be collected for subjects who withdraw from the study after providing informed consent but prior to randomisation onto the study (Screen Failures).

The Baseline visit will be Day 1. Prior to dosing on Day 1, the following assessments will be completed:

- Review of inclusion/exclusion criteria, including eDiary data
- Symptom directed physical examination
- Vital signs (after resting for  $\geq 5$  mins, see Section 10.3.8)
- 12-lead ECG
- Blood samples for clinical chemistry, haematology and plasma bone turnover markers
- Urine sample for urinalysis

- 
- Subjects will be asked to complete the MenQoL-I, HFRDIS, Pittsburg Sleep Quality Index, Insomnia Severity Index, electronic Columbia Suicide Severity Rating Scale (eC-SSRS) and the Beck Depression Inventory II.
  - Review for adverse events and changes in concomitant medications

Eligible subjects will be randomised on Day 1 to NT-814 or placebo. Randomisation will be performed centrally via an interactive web response system (IWRS).

Subjects will be given their first dose of IMP in the clinic and take all subsequent doses at home once a day in the evening (starting the following day) for a total of 12 weeks. At the baseline visit, subjects will be provided with IMP sufficient for the next 4 weeks.

Subjects will continue to complete the eDiary twice a day throughout the study until the Final Follow-up visit at Week 16.

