#### **8.6.6 Interim visits (Weeks 2, 4, 8, and 12)**

During the double-blind treatment phase, subjects will return to the clinic for interim assessments at Weeks 2, 4, 8 and 12. Weeks 2 and 4 should be scheduled within  $\pm 3$  days of the target visit day and Weeks 8 and 12 within  $\pm 4$  days of the target visit day. The visit at Week 12 should be conducted at a similar time of day to the baseline visit to reduce diurnal variation in the plasma bone turnover markers.

At the start of each visit a blood sample will be taken for determination of plasma levels of NT-814. At the same time, if required per the Study Schedule, blood samples for safety laboratory assessments and plasma bone turnover markers will be taken. Subjects will be asked to provide the time they took their dose of study medication on the previous day and this will be recorded on the eCRF.

Study medication compliance will be reviewed at all visits and a new supply of study medication (sufficient for the next 4 weeks) will be provided at Weeks 4 and 8. Diary completion compliance will also be reviewed, and training/re-training provided as necessary.

At each visit the following assessments will be completed:

- Vital signs (after resting for  $\geq 5$  mins, see Section 10.3.8)
- 12-lead ECG
- Blood samples for hematology (Weeks 2, 4 and 12), clinical chemistry (Weeks 2, 4, 8 and 12), pharmacokinetic analysis (Weeks 2, 4, 8 and 12) and plasma bone turnover markers (Week 12 only)
- Urine samples for urinalysis (weeks 2, 4 and 12)

- 
- Subjects will be asked to complete the MenQoL-I, Pittsburgh Sleep Quality Index and Insomnia Severity Index (Weeks 4, 8 and 12), the HFRDIS and Beck Depression Inventory II Weeks 2, 4, 8 and 12) and eC-SSRS (Weeks 4 and 12)
  - Review of eDiary compliance
  - Review for adverse events and changes in concomitant medications

At Week 12, subjects may be re-started on any prohibited medications that are permitted after the end of treatment (see Appendix A).

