## **9.5 Treatment Accountability and Compliance Checks**

In accordance with regulatory requirements, the Investigator or designated site staff must document the amount of IMP dispensed and/or administered to study subjects, the amount returned by study subjects, and the amount received from and returned to the Sponsor (or representative) when applicable. IMP accountability records must be maintained throughout the course of the study. The accountability unit for this study is a capsule. Discrepancies are to be reconciled or resolved. Procedures for final disposition of unused IMP will be provided in the appropriate Study Manual.

The Investigator has overall responsibility in ensuring that the study treatment is received and managed at the study site in accordance with Good Clinical Practice (GCP).

Limited responsibility may be delegated to a nominated study site representative and this delegation must be documented. Study treatment will be dispensed by a nominated person at each study site.

The Sponsor will be permitted upon request to audit supplies, storage and dispensing records and procedures.

Every effort should be made to encourage subject compliance with the dosage regimen as per the protocol. All subjects will be instructed to return their medication carton with any unused capsules at each visit. A record of the capsules dispensed, taken, and returned will be recorded at each visit and compliance calculated.

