**Table 2 Evaluation Intervals for Efficacy and Safety Analysis**

Evaluation	Targeted time point	Protocol-Specified Interval	Interval for Analysis
Screening Visit 1	Day -21	Day -21	Day -18 or earlier
Screening Visit 2*	Day -14	Day -16 to Day -12	Day -17 to Day -4
Baseline	Day 1	Day 1	Day -3 to Day 1
Week 2	Day 15	Day 12 to Day 18	Day 2 to Day 22
Week 4	Day 29	Day 26 to Day 32	Day 23 to Day 43
Week 8	Day 57	Day 53 to Day 61	Day 44 to Day 71
Week 12	Day 85	Day 81 to Day 89	Day 72 to Day 99
Week 16 FU	Day 113	Day 108 to Day 118	Day 100 or later

\* At least 6 days after Screening Visit 1 to allow at least 6 days of paper diary data to be completed. Study day is calculated per section 4.2.8.

In case more than one measurement per time period is captured, the closest to the targeted time point will be considered for analysis. If two measurements occur at the same distance from the target day for a particular analysis window then the first measurement will be considered for analysis. Unscheduled visits will be taken into account. In case of withdrawal, all data from the early termination visit will be assigned under its corresponding analysis visit according to its day.

Actual dates and times will be used for pharmacokinetic summaries rather than nominal days and times.

Any visits occurring outside visit windows defined in the protocol should be recorded as a PD and will be reviewed at the BDRM to assess on an individual case by case basis to which visit the data should be allocated.

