**Table 3 Exposure variables definitions**

Variables	Definitions
Duration of dosing (days)	Last dose of randomised blinded treatment – first dose of randomised blinded treatment +1
Duration of dosing (weeks)	(Last dose of randomised blinded treatment – first dose of randomised blinded treatment +1) / 7

Study treatment compliance (%)	
<math>100 * (\text{total number of capsules taken}) / (\text{total number of capsules planned to be taken})</math>
 
Note: number of capsules planned to be received is 4*duration of dosing (in days).
 
Total number of capsules taken is calculated using the eCRF pages ‘Drug Accountability’ and ‘IMP dispense/administration’, based on the fact that each weekly card contains 32 capsules and four weekly cards will be dispensed at each of baseline, week 4 and week 8. Thus, one visit dispensed kit contains <math>32*4=128</math> capsules. At subsequent Visits (Weeks 4, 8 and 12) the number of capsules remaining within the 4 weekly cards is recorded and the number of capsules taken = <math>128 - \text{Number of capsules remaining in the 4 weekly cards}</math>.
 
In the event that the subject doesn’t return some or all of the 4 weekly cards at Week 4, 8 or 12, it will not be possible to determine the number of capsules taken, so protocol medication adherence taken will be set as missing. In the event that more than one kit was dispensed to the subject between 2 visits, in a same way it will not be possible to determine the number of capsules taken, so protocol medication adherence taken will be set as missing. Unscheduled visits will be also included in the calculation if Drug Accountability eCRF Form is completed.

Cumulative NT-814 exposure (mg)	
It is assumed that on a day the subject takes the 4 planned capsules:
 
In Placebo group, Cumulative dose = 0
 
In NT-814 40mg group, Cumulative dose = <math>(\text{number of capsules taken} / 4) * 40 \text{ mg}</math>.
 
In NT-814 80mg group, Cumulative dose = <math>(\text{number of capsules taken} / 4) * 80 \text{ mg}</math>.
 
In NT-814 120mg group, Cumulative dose = <math>(\text{number of capsules taken} / 4) * 120 \text{ mg}</math>.
 
In NT-814 160mg group, Cumulative dose = <math>(\text{number of capsules taken} / 4) * 160 \text{ mg}</math>.

The following information will be tabulated overall and by treatment:

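### A 32-dose carton does not cover an early visit followed by a late one (up to 35 doses from Week 4 to Week 8, up to 36 from Week 8 to Week 12), and SAP Table 3 sets compliance to missing when a second kit is given between visits

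*Protocol*

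**What the plan says.** Protocol Section 9.4 commits to supply that lasts, both for the run-in dispensing and for the three double-blind ones: "subjects will be dispensed sufficient IMP for daily dosing at home until the next visit, with overage included to allow for visit windows". Protocol Section 9.2 fixes the quantity. A double-blind carton has four weekly cards of 7 + 1 days and so provides "sufficient capsules for a 4-week dosing period (plus 4 days overage to allow for delays in clinic visit scheduling". SAP Table 3 agrees: 128 capsules at each of Baseline, Week 4 and Week 8, at four capsules a day.

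Visit windows are set around fixed target days, not around the previous visit (Protocol Table 10-1, SAP Table 2). Week 4 runs from Day 26 to Day 32, Week 8 from "Day 53 to Day 61", and Week 12 from Day 81 to Day 89. The last dose falls on the evening before the Week 12 visit (Protocol Section 9.4).

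On leftovers, Section 9.4 says: "Subjects will return any unused medication at each clinic visit". Section 8.6.6 has a new four-week supply issued at Weeks 4 and 8. Section 9.5 adds: "A record of the capsules dispensed, taken, and returned will be recorded at each visit and compliance calculated".

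SAP Table 3 counts capsules taken per kit, as 128 minus those remaining. It sets adherence to missing in the event that "more than one kit was dispensed to the subject between 2 visits". The same cell brings unscheduled visits into the calculation when the accountability form has been completed. SAP Section 3.2 makes compliance below 80% a derived protocol deviation (PD 4.2) and says that the IMP data should not be missing.

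**The concern.** Four days of overage allow for one late visit after an on-time one. They do not allow for an early visit followed by a late one, because the two displacements add. A subject could keep every visit window and still run out of drug, contrary to Section 9.4. The undosed evenings would be the last ones before the visit, inside the seven-day diary window used for the Week 8 or Week 12 hot flush endpoints.

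The natural remedy, a second carton, then meets the SAP Table 3 rule that sets compliance to missing. A fully dosed subject who was properly resupplied could lose her compliance value, although the capsule counts needed to compute it are collected.

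**Working it through.** **Inputs.** Doses per carton come from Protocol Section 9.2 and SAP Table 3, windows from Protocol Table 10-1 and SAP Table 2. Study days have no Day 0 (SAP Section 4.2.8).

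**The plan's own figure.** 4 cards x 8 days x 4 capsules = 128 capsules = 32 daily doses. This matches SAP Table 3.

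**Doses needed.** For dispensing on Day a and the next visit on Day b, the evenings to cover are Day a to Day b - 1, so the need is b - a.

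| Dispensing | Largest need | Supplied | Covered? |
|---|---|---|---|
| Run-in | Day -16 to Day -1 = 16 | 2 x 8 = 16 | yes |
| Baseline to Week 4 | 32 - 1 = 31 | 32 | yes |
| Week 4 to Week 8 | 61 - 26 = 35 | 32 | short by up to 3 |
| Week 8 to Week 12 | 89 - 53 = 36 | 32 | short by up to 4 |

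**Which visit pairs fall short.**
- Week 4 to Week 8: 3 + 2 + 1 = 6 of 7 x 9 = 63 in-window day-pairs need more than 32 doses.
- Week 8 to Week 12: 4 + 3 + 2 + 1 = 10 of 9 x 9 = 81.
- Of the 567 combinations of Week 4, 8 and 12 visit days, none is short in both intervals.
- If both visits fall within 2 days of target, the need is at most 28 + 2 + 2 = 32, and no shortfall is possible.

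These are counts of day combinations, not probabilities. If visit days were independent and evenly spread over the windows, the shares would be 6/63 = 9.5% and 10/81 = 12.3%. If visits stayed within 2 days of target, both would be 0%.

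**If the subject simply runs out.** A Week 8 to Week 12 shortfall needs a Week 8 visit on Day 53 to 56. Doses taken are then (Week 8 day - 1) + 32 = 84 to 87. Section 8.6.5 specifies dosing "once a day in the evening (starting the following day) for a total of 12 weeks", that is 84 days, so the nominal course is still complete. Measured against the evenings due up to the Week 12 visit, the worst case is 84 of 88 = 95.5%, far above 80%.

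**Effect on the Week 12 frequency endpoint, under harsh assumptions.** Take even spread, perfect adherence and full loss of effect on each undosed night. Mean undosed nights = (4 x 1 + 3 x 2 + 2 x 3 + 1 x 4)/81 = 20/81 = 0.25. Multiplying by 4/7, the assumed 4-flush difference averaged over 7 days, gives 0.14 flushes against an SD of 4.4. With visits near target the figure is 0.

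**If leftovers are kept.** By Week 8 at most 60 of 64 doses are needed, and by Week 12 at most 88 of 96. Keeping only the leftovers from the Week 4 carton at Week 8 is also enough: 89 - 26 = 63 of 64.

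**Compliance with a second carton.** Take visits on Days 26, 53 and 89, with two cartons given at Week 8.
- Dispensed: 128 + 128 + 256 = 512.
- Returned: 4 x (32 - 25) = 28, 4 x (32 - 27) = 20 and 4 x (64 - 36) = 112, in total 160.
- Taken: 512 - 160 = 352 = 4 x 88, which is 100% of the doses due.

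Read as applying to two cartons handed out together, the Table 3 rule reports this subject as missing.

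**The case against.** The strongest objection concerns leftovers. The return wording in Section 9.4 also covers Week 2, where no drug is dispensed. If return always meant surrender, nobody would have capsules from Week 2 to Week 4, so at Week 2 it must mean bring back, count and keep. No text forbids the same at Weeks 4 and 8, and with leftovers kept nobody falls short. This stands in part. Surrender is an inference, although the new supply at Weeks 4 and 8 and the per-kit count in SAP Table 3 both treat a kit as closed at the next visit.

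The IWRS settings and the Study Manual might also handle long intervals. They are not among the documents, and this lowers confidence. They would not alter the SAP rule.

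On that rule, a subject who runs low and returns at an unscheduled visit with the form completed may keep her compliance value. That is a fair reading. It does not reach two cartons handed out at one scheduled visit, which no section describes and which requires the site to know in advance that the next visit will be late.

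A reader might infer that resupplied subjects drop out of the PP set. The documents do not support that. A missing value is not a value below 80%, SAP Section 3.2 attaches no exclusion to missing compliance, and relevance is settled around the blinded data review. A reader might also take the day-pair shares as expected frequencies. They are not, since the plan says nothing about how visits scatter.

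**Conclusion.** The concern holds as a minor inconsistency, with moderate confidence. The supply commitment in Section 9.4 is not met by a 32-dose carton in two of four dispensings: up to 3 doses short before Week 8 and up to 4 before Week 12. It arises only when an early visit precedes a late one and only if leftovers are surrendered. How often that happens is unknown and may be near zero.

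A claim of damage to the efficacy results would go too far. The Week 4 co-primary endpoints are untouched, because Baseline to Week 4 is covered. Even the harsh illustration moves the Week 12 difference by only 0.14 flushes, and no run-out approaches the 80% threshold. No exclusion from the PP set is established. Apart from the unmet commitment, what remains is a compliance rule that discards a value which the recorded counts would usually allow to be computed.

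**What to change.** 1. **Protocol Section 9.4.** When the next visit will be more than 32 days away, let the subject keep her leftover capsules or resupply her. State whether capsules brought back at Weeks 4 and 8 may be kept. A maximum gap of 32 days between visits is an option only. It excludes no target day (26 + 32 = Day 58 against target 57; 53 + 32 = Day 85 against target 85), but it would turn 6 of 63 and 10 of 81 currently permitted day-pairs into deviations.
2. **SAP Table 3.** Replace the rule on more than one kit between two visits with total capsules dispensed minus total capsules finally returned, over all kits. Counting only final returns avoids subtracting kept capsules twice. Keep missing only for cards that are not returned.

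The cost is slightly more accountability work and an occasional extra carton. No additional subjects, scheduled visits or data items are needed, because capsules dispensed and returned are already recorded.
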